3. PLANNED ANALYSES

3.1. Interim Analyses

There are no interim analyses planned for this study.

3.2. Final Analyses

The final planned analyses will be performed after all required database cleaning activities have been completed and final database release (DBR) and database freeze (DBF) has been declared by Data Management.

4. ANALYSIS POPULATIONS

Population	Definition / Criteria	Analyses Evaluated
Intent-To-Treat (ITT)	
 All subjects who signed informed consent form, were randomised and who had at least one post-baseline assessment on primary endpoints, second endpoints, and/or exploratory endpoints. The ITT population will be the primary population of interest. 	Study Population Efficacy
Per-Protocol (PP)	
 All subjects in the ITT population with no major protocol deviations and with $\geq 80\%$ treatment compliance and diary compliance. The PP population will not be analyzed if this population comprises more than 95% or less than 50% of the ITT population. Only the primary efficacy variables will be analyzed using the PP population. 	Efficacy
Safety	
 All subjects who are enrolled into the study and who have at least one DRC assessment. 	Safety

Refer to [Appendix 8](#): List of Data Displays which details the population used for each display.

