7.1. Time and Events Table

ACTIVITY	Visit 0	Visit 1	Visit 2	Visit 3	Visit 4	Visit 5	Visit 6 (or Early Withdrawal)
Study Week (Visit Window)	0	4w±1	8w±1	12w±1	16w±1	20w±1	24w±1
Informed consent	x						
Randomization/Allocation of clusters	x						
Subject Demography	x						
Medical history	x						
Verification of inclusion/exclusion criteria	x						
Efficacy Evaluation							
Verification of withdrawal criteria		x	x	x	x	x	x
Issue diary record cards	x	x	x	x	x	x	
Collect/Review diary record cards		x	x	x	x	x	x
Compliance assessment		x	x	x	x	x	x
Asthma control Test (ACT) score	x	x	x	x	x	x	x
AQLQ(S)	x						x
Lung function Test	x						x
Safety Evaluation							
Adverse event assessment ¹	x	x	x	x	x	x	x

1. Serious AEs will be recorded from the time the consent form is signed until the follow-up visit. All AEs will be recorded from the start of study treatment until the follow-up visit.

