7.4.1.1. Time period and Frequency for collecting AE and SAE information

- The investigator or site staff is responsible for detecting, documenting and reporting events that meet the definition of an AE or SAE.
- Serious AEs will be recorded from the time the consent form is signed until the follow-up contact. All AEs will be recorded from the start of study treatment until the follow-up contact.
- Medical occurrences that begin prior to the start of study treatment but after obtaining informed consent may be recorded on the Medical History/Current Medical Conditions section of the CRF.
- Any SAEs assessed as related to study participation (e.g., protocol-mandated procedures, invasive tests, or change in existing therapy) or related to a GSK product will be recorded from the time a subject consents to participate in the study up to and including any follow-up contact.
- All SAEs will be recorded and reported to GSK within 24 hours, as indicated in [Appendix 2](#).

- Once the investigator determines that an AE is identified as explicitly attributed to any GSK product (including products not covered in the specific study objective), the adverse drug reactions (ADR) page should be completed and reported to GSK China within 5 calendar days. Any follow-up information on a previously reported ADR will also be reported to GSK China within 5 calendar days.
- Investigators are not obligated to actively seek AEs or SAEs in former study subjects. However, if the investigator learns of any SAE, including a death, at any time after a subject has been discharged from the study, and he/she considers the event reasonably related to the study treatment or study participation, the investigator must promptly notify GSK.

NOTE: The method of recording, evaluating and assessing causality of AEs and SAEs plus procedures for completing and transmitting SAE reports to GSK are provided in [Appendix 2](#).

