9.3.1. Analysis Populations

Three populations are defined for this study.

- Intent-to-Treat (ITT) Population: all subjects who signed informed consent form, were randomised and who had at least one post-baseline assessment. The ITT population will be the primary population of interest.
- Per Protocol (PP) Population: all subjects in the ITT population with no major protocol deviations and with $\geq 80\%$ treatment compliance and diary compliance. The PP population will not be analyzed if this population comprises more than 95% or

less than 50% of the ITT population. Only the primary efficacy variables will be analyzed using the PP population.

- Safety Population: all subjects who are enrolled into the study and who have at least one DRC assessment.

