8. SAFETY ANALYSES

The safety analyses will be based on the Safety population, unless otherwise specified.

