8.1. Adverse Events Analyses

The number (%) of subjects in each treatment group with treatment emergent AEs will be produced. Counts and percentages will also be presented of subjects with serious adverse events (SAEs), AEs leading to withdrawal, AEs by severity, AEs by relationship to study procedure/study drug, asthma exacerbation and death.

Adverse events will be coded by MedDRA version 21.0 or above. Adverse events will be summarized and presented by system organ class (SOC) and preferred term (PT) by treatment group. Adverse events analyses including the analysis of AEs, SAEs, non-serious AE and other significant AEs will be summarized. All AEs and SAEs will be listed. The details of the planned displays are provided in [Appendix 8: List of Data Displays](#).

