10.5. Appendix 5: Reporting Standards for Missing Data

10.5.1. Premature Withdrawals

Element	Reporting Detail
General	
 • Subject study completion (i.e. as specified in the protocol) was defined as who has completed all visits of the study. • Withdrawn subjects were not replaced in the study. • All available data from participants who were withdrawn from the study will be listed and all available planned data will be included in summary tables and figures, unless otherwise specified. • Withdrawal visits will be slotted as per Appendix 2: Schedule of Activities or will be summarised as withdrawal visits.

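### The Safety population requires at least one diary assessment, so by default a subject with an early serious event or death and no diary data is left out of the tabulated safety counts

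*SAP*

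**What the plan says.** SAP Section 4 gives the Safety population as "All subjects who are enrolled into the study and who have at least one DRC assessment". Protocol 9.3.1 has the same rule: "all subjects who are enrolled into the study and who have at least one DRC assessment". SAP Section 8 then sets the default: "The safety analyses will be based on the Safety population, unless otherwise specified".

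On collection, Protocol 7.4.1.1 states: "Serious AEs will be recorded from the time the consent form is signed until the follow-up contact". In the Time and Events Table (Protocol 7.1, repeated in SAP Appendix 2), cards are issued from Visit 0. The row "Collect/Review diary record cards" is first marked at Visit 1 (week 4 ± 1), and its last column is Visit 6 or early withdrawal.

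On reporting, SAP 8.1 promises: "Counts and percentages will also be presented of subjects with serious adverse events (SAEs), AEs leading to withdrawal", and goes on to include asthma exacerbation and death. The same section adds: "All AEs and SAEs will be listed". SAP 10.5.1 has a general rule for withdrawals: "All available data from participants who were withdrawn from the study will be listed and all available planned data will be included in summary tables". That rule carries its own exception for anything specified elsewhere. SAP 10.5.2 requires the study report to document any participant excluded from summaries or analyses, with the reason.

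**The concern.** Entry to the safety set depends on an efficacy instrument, a paper diary for peak flow, symptoms and medication. Safety events are captured by other routes: open questioning at visits, the SAE pages, and a dedicated death form (Protocol 7.4.1.2 and 7.4.1.4). An event can therefore be fully recorded while the subject fails the population rule.

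The exclusion is also related to outcome. A subject who dies or is admitted in the first weeks is less likely than others to hand in a card. Protocol 5.3 adds to this, because a protocol-defined exacerbation leads to discontinuation, so some subjects with events leave early. At stake are the tabulated numbers of subjects with SAEs, deaths and AEs leading to withdrawal. The study is open-label and allocated by centre, so diary return could differ between arms, although nothing in the documents shows that it would.

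**Working it through.** The documents give no SAE rate and no rate of diary non-return, so there is no plan figure to reproduce. The check is to follow one subject through the rules and then show what the rule does to a table.

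**Tracing the rule**

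1. The subject consents at Visit 0. SAE recording starts and a diary card is issued.
2. Before Visit 1 the subject has a serious event. It is recorded as an SAE, and if fatal the death form is completed.
3. If the subject later attends any visit, including early withdrawal, and hands in a card with an entry, the condition is met and the subject is in the Safety population.
4. If the subject dies, stays in hospital or is lost before any card is collected, there are no diary data. The term DRC assessment is not defined, but a card filled in and never returned leaves nothing to analyse, so the result is the same.
5. The subject then falls outside the Safety population and, by the SAP Section 8 default, outside the SAP 8.1 counts. The SAP text states no exception for AEs, SAEs or deaths.

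**Contrast with ITT.** SAP Section 4 admits a subject to ITT on any post-baseline primary, secondary or exploratory assessment. A subject with a Visit 1 ACT and no diary entry is in ITT but not in Safety. A hospitalised exacerbation in that subject could count in the exploratory analysis (SAP 7.3) and be absent from the SAE table.

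**Effect on a table.** Let N be subjects enrolled, E subjects with an SAE, k subjects without a diary, and e those of the k who had an SAE. The table shows E − e subjects out of N − k.

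- The count can only stay the same or fall, by exactly e.
- The percentage falls only if e/k > E/N. Otherwise it is unchanged or rises.

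Take N = 528 (planned enrolment, Protocol 9.2.1) and assume E = 11, so E/N = 11/528 = 2.1%. If every subject without a diary had an SAE (k = e):

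| e | Tabulated | Rate |
|---|---|---|
| 0 | 11/528 | 2.1% |
| 1 | 10/527 | 1.9% |
| 2 | 9/526 | 1.7% |
| 3 | 8/525 | 1.5% |
| 5 | 6/523 | 1.1% |

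At the other extreme, assume 5% never return a diary (528 × 0.05 ≈ 26) and none of them had an SAE. The table then shows 11/(528 − 26) = 11/502 = 2.2%, slightly above the true 2.1%. The direction is certain for counts but not for percentages.

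**The case against.** Several points on the other side stand.

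- **Early withdrawal visit.** Cards are also collected there, and Protocol 5.3 requires the discontinuation procedures when a subject leaves. Subjects who withdraw for an event and attend with a card stay in the set, as do those admitted early who return a card later.
- **Low threshold.** Diaries are completed twice daily (Protocol 4.2), and a single assessment is enough.
- **Default only.** SAP Section 8 allows exceptions. SAP Section 4 says Appendix 8 gives the population for each display, and Appendix 8 points to a mock-shell file that is not among the documents. A reader might infer that these subjects vanish from every safety table. The documents establish the default, not each table.
- **Other records.** The promise to list all AEs and SAEs is unqualified and can be read as an exception to the default. SAP 10.5.1 also lists withdrawn subjects' data, SAP 10.5.2 requires exclusions to be documented, and SAEs reach the sponsor within 24 hours. A reader might infer that the events are lost from reporting altogether. The text does not support that.
- **Limited reach.** Protocol Section 3 lists no safety objective and the trial supplies no treatment, so the primary conclusion is not affected.

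What does not stand is that these safeguards remove the problem. A listing or a note on exclusions does not change a tabulated count. The SAP 10.5.1 rule on summary tables yields to anything specified elsewhere, and the Safety definition is such a specification.

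**Conclusion.** The point holds as a defect in the default rule. A subject who dies, stays in hospital or is lost before any card is collected can have a recorded SAE or death and be omitted from the SAP 8.1 counts. Those counts can only be too low. The percentages may move either way, depending on whether subjects without a diary have more events than the rest.

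The number affected is probably small and cannot be estimated from the documents. A reader might assume that 2% to 5% of 528 never return a diary and cite 11 to 26 subjects (528 × 0.02 ≈ 11; 528 × 0.05 ≈ 26). That range is an assumption, and it counts subjects without a diary, not subjects with events, so it does not measure lost SAEs. The illustration above likewise rests on an assumed 11 subjects with an SAE. It shows only that when events are few, omitting two or three is visible in the table.

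The conclusion assumes that the mock shells do not name a wider population for the AE, SAE and death tables. A correction is worth making because the exclusion is related to outcome, has no stated rationale and is easily avoided.

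**What to change.** Preferred: in Protocol 9.3.1 and SAP Section 4, define the Safety population as all consented subjects enrolled at a randomised centre, and delete the diary condition.

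Minimum: add one sentence to SAP Section 8 stating that AEs, SAEs and deaths are tabulated for all enrolled subjects, whether or not diary data exist, and make the mock shells agree.

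Neither option needs new data or changes any efficacy analysis. The preferred option is one line in each document, but the protocol line is an amendment and goes to ethics review as applicable (Protocol 10.2). The minimum option needs only the SAP sentence and a check of the shells.

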4.1. Protocol Deviations

Important protocol deviations (including deviations related to study inclusion/exclusion criteria, conduct of the trial, patient management or patient assessment) will be summarised and listed.

Important deviations, which result in exclusion from the analysis population, will also be summarised and listed. Protocol deviations will be tracked by the study team throughout the conduct of the study in accordance with the Protocol Deviation Management Plan (refer to [Appendix 1](#)).

- Data will be reviewed prior to freezing the database to ensure all important deviations and deviations which may lead to exclusion from the analysis are captured and categorised on the protocol deviations dataset.
- This dataset will be the basis for the summaries and listings of protocol deviations.

A separate summary and listing of all inclusion/exclusion criteria deviations will also be provided. This summary will be based on data as recorded on the inclusion/exclusion page of the eCRF.

4.2. Diary Compliance

Subjects’ diary compliance will be assessed by the records of diary cards. For the subjects to be included in the PP population, there should be at least $\geq 80\%$ expected diary counts in the diary cards according to the visits they have completed.

4.3. Treatment Compliance

Subjects’ treatment compliance will be calculated as follow:

Treatment compliance = $\frac{\text{Number of days that the subjects take asthma drugs following the doctor's advice}}{\text{The last assessment date in the diary cards} - \text{the first assessment date in the diary cards} + 1} \times 100\%$

The number of days that the subjects take asthma drugs following the doctor’s advice will be captured in the diary cards. For the subjects to be included in the PP population, the treatment compliance should $\geq 80\%$.

5. CONSIDERATIONS FOR DATA ANALYSES AND DATA HANDLING CONVENTIONS

Continuous data will be summarized by treatment using descriptive statistics: number of subjects/observations (n), arithmetic mean values (Mean), median value (Median), standard deviation (SD), minimum value (Min), and maximum value (Max). Min and Max will be presented with the same number of decimal places as the raw data recorded in the database. Mean and Median will be presented using one more additional decimal place. SD will be presented with two more decimal places than the raw data recorded in the database.

Categorical data will be summarized by treatment using frequencies and percentages. Counts and percentages will be presented for each category. Percentages will be presented to one decimal place.

Statistical tests of treatment effects will be performed at a 2-sided significance level of 0.05, unless otherwise stated. And all p-values will be rounded up to 3 decimal places.

5.1. Study Treatment Display Descriptors

Code	Description	Order in TLF
ACT	Asthma Control Test	1
UC	Usual Care	2

Treatment comparisons will be displayed as follows using the descriptors as specified: ACT vs UC.

5.2. Baseline Definitions

For primary endpoint, baseline will be the measurements taken at visit 0. For secondary endpoints, baselines of FEV1 and AQLQ(S) will be the measurements taken at visit 0; for symptom score and PEF, baselines are unavailable since the data will be collected daily using diary cards from the first day of asthma treatment and baseline assessments before treatment will not be conducted.

Unless otherwise stated, if baseline data is missing, no derivation will be performed and baseline will be set to missing.

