4.2. Treatment Arms and Duration

- The study is planned to be a 24-week study.
- Baseline (week 0, visit 0): Subjects eligible for inclusion criteria will sign informed consent form at Visit 0. At this visit, investigators should collect baseline data, including demographic data (gender, age, height, weight, education level and smoking history), history of asthma (disease duration, disease severity and exacerbation history), and past and concurrent medical conditions and medication (both asthma and non-asthma). ACT, AQLQ(S) and lung function test will be completed as the baseline measurement in sequence.
- Treatment period (week 0-week 24): a 24 week treatment period. Subsequent scheduled visits occur as follows: Week 4 (Visit 1), Week 8 (Visit 2), Week 12 (Visit 3), Week 16 (Visit 4), Week 20 (Visit 5) and Week 24 (Visit 6).
- In this cluster-randomization design, each study centre, considered as a cluster, will be randomized to either ACT guided treatment group or control group (usual care group). The randomization will be stratified according to the hospital level (Tier 3 vs. Tier 2). The hospital level is determined in accordance with the uniform requirements of the government. And a Tier 3 hospital is on a larger scale and provides superior medical care than a Tier 2 hospital.
- For the subjects who are recruited in the ACT centres, they will be treated based on the ACT score. For subjects who are recruited in the control centres, they will be treated based on doctor's subjective judgment.

Table 1 ACT-guided treatment

ACT score	Treatment adjustment
ACT=25, ≥ 3 months	Step-down treatment
ACT ≥ 20 , <25 or ACT=25, <3 months	No change

ACT score	Treatment adjustment
ACT \leq 19	Step-up treatment

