7.3.2. Secondary Endpoint (s)

- Mean daytime symptom score over the 24-week treatment period
- Mean night-time symptom score over the 24-week treatment period
- Mean change from baseline to the end of study in FEV₁
- Mean morning(AM) PEF over the 24-week treatment period
- Mean evening(PM) PEF over the 24-week treatment period
- Mean change from baseline to the end of study in AQLQ(S) score
- Time to first ACT score ≥ 20 or improvement of more than 3 points in ACT over the 24-week treatment period

Asthma symptom score

Subjects will be instructed to record daytime and night-time asthma symptom scores prior to taking the morning or evening dose of study medication or rescue medication. Any asthma-related symptoms, such as wheeze, shortness of breath, cough or chest tightness experienced during the previous 12 hours will be rated as follows. The following will be recorded on DRC.

Daytime symptom score

0 = No symptoms during the day

1 = Symptoms for one short period during the day

2 = Symptoms for two or more short periods during the day

3 = Symptoms for most of the day which did not affect my daily activities

4 = Symptoms for most of the day which did affect my normal daily activities

5 = Symptoms so severe that I could not go to work or perform normal daily activities

Night-time symptom score

- 0 = No symptoms during the night
- 1 = Symptoms causing me to wake once or wake early
- 2 = Symptoms causing me to wake twice or more (including waking early)
- 3 = Symptoms causing me to be awake for most of the night
- 4 = Symptoms so severe that I did not sleep at all

FEV₁

FEV₁ will be measured at visit 0 and 6. Subjects should refrain from using short-acting bronchodilators for at least 6 hours prior to performing FEV₁ measurements. The highest of three technically acceptable measurements of FEV₁ will be taken.

Peak Expiratory Flow (PEF)

At Visit 0, the subject will be given a Mini-Wright Peak Flow Meter and taught how to measure and record their PEF. At each visit, the subjects' ability to measure their PEF will be checked and, if the investigator has any concerns, the subject will be retrained. The instructions for use will be provided with each Peak Flow Meter. PEF should be measured while subject is in the sitting position.

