7.2. Secondary Efficacy Analyses

7.2.1. Endpoint / Variables

- Mean daytime symptom score over the 24-week treatment period
- Mean night-time symptom score over the 24-week treatment period
- Mean change from baseline to the end of study in FEV1
- Mean morning (AM) PEF over the 24-week treatment period
- Mean evening (PM) PEF over the 24-week treatment period
- Mean change from baseline to the end of study in AQLQ(S) score
- Time to first ACT total score ≥ 20 or improvement of more than 3 points in ACT total score over the 24-week treatment period
- Time to first ACT total score ≥ 20 and improvement of more than 3 points in ACT total score over the 24-week treatment period

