7.2.2. Analysis Methods

All secondary endpoints will be confined to the ITT population. The continuous efficacy endpoints will be summarized by mean, standard deviation (SD), median, minimum and maximum according to scheduled visits. Time to event endpoint will be summarized by median time, 95% confidence interval of median time, lower and upper quantiles and range.

Continuous efficacy endpoints will be analysed using analysis of covariance (ANCOVA) and adjusted for centre as a random effect.

For mean daytime and night-time symptom score and mean morning and evening PEF, the mean values will be based on the available data on the diary card over each visit assessment period. No imputations will be performed on missing data. The mean values will be considered missing if less than 14 days are recorded in each visit assessment period. A Mixed Model Repeated Measures (MMRM) will be used with covariates of treatment, centre, type of baseline controller (ICS vs. ICS/LABA), gender and age, with the centre as a random factor. The results will be presented as LS mean (SE), 95% confidence interval for LS mean, treatment difference, 95% confidence interval for treatment difference and P-value by visit.

The example SAS codes are as below:

```
proc mixed data=input_data;
class invsite rndgrp visit subjid blcontrol gender;
model endpoint=rndgrp actbl blcontrol gender age/ ddfm =kr;
random intercept/subject= invsite;
repeated visit / subject=subjid type=un;
lsmeans rndgrp*visit / cl diff e;
ods output lsmeans=lsmeans;
ods output diffs=diffs;
run;
quit;
```

where `input_data` is the name of the input dataset and `endpoint` is the endpoint variable. In terms of the covariates `rndgrp`, `actbl`, `blcontrol`, `gender` and `age` are variables for randomised treatment code, baseline ACT total score, type of baseline controller, gender and age respectively. For random effect, `invsite` is variable for centre. For repeated measures, `visit` is variable for visit number and `subjid` is variable for subject's ID.

The AQLQ(S) contains 32 items in four domains: activity limitation (11 items), symptoms (12 items), emotional function (5 items) and environmental stimuli (4 items). The following items are included in each of the 4 domains:

- Symptoms: 6, 8, 10, 12, 14, 16, 18, 20, 22, 24, 29, 30
- Activity Limitation: 1, 2, 3, 4, 5, 11, 19, 25, 28, 31, 32
- Emotional Function: 7, 13, 15, 21, 27
- Environmental Stimuli: 9, 17, 23, 26

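### The PEF and symptom diary endpoints have no pre-treatment value, and their model leaves out Visit 0 FEV1, height and AQLQ(S) symptom data that could modestly sharpen the comparison

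*SAP*

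**What the plan says.** SAP 5.2 takes Visit 0 as baseline for ACT, FEV1 and AQLQ(S). For symptom score and PEF it says that "baselines are unavailable since the data will be collected daily using diary cards from the first day of asthma treatment" and that "baseline assessments before treatment will not be conducted". The endpoints are accordingly on-treatment averages, for example "Mean morning (AM) PEF over the 24-week treatment period" (SAP 7.2.1), and not changes from baseline.

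The analysis is in SAP 7.2.2. The text reads: "A Mixed Model Repeated Measures (MMRM) will be used with covariates of treatment, centre, type of baseline controller (ICS vs. ICS/LABA), gender and age", with centre random. The example code reads: "model endpoint=rndgrp actbl blcontrol gender age/ ddfm =kr". The code and its variable key therefore contain baseline ACT, and the text does not.

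Other Visit 0 information exists. Protocol 4.2 says that "ACT, AQLQ(S) and lung function test will be completed as the baseline measurement in sequence" and lists "demographic data (gender, age, height, weight, education level and smoking history" among the data collected. Protocol 7.3.2 schedules FEV1 at Visits 0 and 6. SAP 7.2.2 defines a 12-item AQLQ(S) symptom domain. On PEF itself, Protocol 7.3.2 says only: "At Visit 0, the subject will be given a Mini-Wright Peak Flow Meter and taught how to measure and record their PEF".

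**The concern.** The four diary endpoints are the only endpoints for Symptoms and PEF, two of the five parameters under the single secondary objective. A comparison of on-treatment means has no subject-level starting value to set against it. The early diary days cannot supply one: subjects enter with ACT below 20, Protocol Table 1 calls for a treatment change in the ACT arm at that level, and control centres follow the physician's judgement, so care may differ between arms from Visit 0.

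Only 12 centres are randomised, six per arm, stratified by hospital tier alone. The study is open-label and subjects are recruited within centres assigned to one arm or the other. Two consequences follow. Subject-level variance that Visit 0 data could explain is left in the residual. And if recruitment differs between arms in ways that gender, age, controller type and (in the code) ACT do not capture, that difference cannot be separated from the effect of ACT guidance. Baseline ACT may be a limited adjuster: the eligibility criteria largely confine it to 12-19, and it is a questionnaire, not a lung-function measure.

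**Working it through.** **1. The plan's own figures.** Protocol 9.2.1 gives 6 centres per arm, 35 evaluable subjects per centre, ICC 0.01, and rates of 29% and 44%. The design effect is 1 + 34 × 0.01 = 1.34. The unpooled two-proportion size is 157.8 per arm; × 1.34 = 211.4 per arm, or 423 in total, against the stated 420. For dropout, 35/0.8 = 43.75, rounded up to 44, and 44 × 12 = 528. These figures reproduce, but they concern the primary endpoint. The documents state no SD, ICC, effect size or power for the diary endpoints, so only the layout (6 × 35 = 210 per arm) is carried forward. Everything below is in SD units with assumed ICCs and correlations.

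**2. Covariates in the diary model.**

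| Term | Collected at Visit 0 | SAP 7.2.2 text | SAP 7.2.2 code |
|---|---|---|---|
| Controller type, gender, age | yes | yes | yes |
| Centre (random) | n/a | yes | yes |
| Baseline ACT | yes | no | yes |
| FEV1 | yes | no | no |
| Height | yes | no | no |
| AQLQ(S) symptom domain | yes | no | no |

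**3. Precision gain.** The variance of an arm mean, in SD² units, is ICC/6 + (1 − ICC)/210.

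- ICC 0.01: 0.001667 + 0.004714 = 0.006381. The subject-level share is 73.9%. SE of the difference = √(2 × 0.006381) = 0.113 SD.
- ICC 0.05: 0.008333 + 0.004524 = 0.012857. The subject-level share is 35.2%. SE of the difference = √(2 × 0.012857) = 0.160 SD.

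Suppose a covariate correlates r with the outcome and removes r² of the subject-level part only. The SE is then multiplied by √(1 − share × r²).

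| ICC | r = 0.5 | r = 0.7 |
|---|---|---|
| 0.01 | √(1 − 0.739 × 0.25) = 0.903, a fall of 9.7% | √(1 − 0.739 × 0.49) = 0.799, a fall of 20.1% |
| 0.05 | √(1 − 0.352 × 0.25) = 0.955, a fall of 4.5% | √(1 − 0.352 × 0.49) = 0.910, a fall of 9.0% |

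Here r should be read as the correlation left after the terms already in the model. Height overlaps with gender, for instance, so a raw correlation would overstate the gain.

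**4. How far a proxy reduces a starting difference.** The 95% range for a chance starting difference is 1.96 × 0.113 = ±0.22 SD at ICC 0.01 and 1.96 × 0.160 = ±0.31 SD at ICC 0.05. If pre-treatment and on-treatment values correlate 0.7 (assumed), about ±0.15 and ±0.22 SD carries forward. A Visit 0 proxy that correlates q with the missing diary baseline cuts this by 1 − √(1 − q²): about 5% at q = 0.3, 13% at 0.5 and 29% at 0.7. Proxies therefore help, but they do not recover the missing baseline.

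**The case against.** The case for leaving the plan alone has real weight. The SAP discloses the absence of a diary baseline, and on-treatment means are a legitimate endpoint. These are secondary endpoints; the primary model already has baseline ACT and its square. Lung function and quality of life each have a separate change-from-baseline endpoint. Protocol 6.1 asks each centre for consecutive patients, which limits selective recruitment, and SAP 6.1 summarises baseline characteristics, so a gross imbalance would be visible.

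The strongest objection concerns chance imbalance. A reader might infer that the comparison carries any starting difference in full. On an assumed SD of 100 L/min, the ranges in step 4 would be ±22 to ±31 L/min passing straight into the PEF result. The documents do not support that reading. They give no SD. It takes the correlation between starting and on-treatment values to be 1, and it ignores gender, age and controller type in the model, ACT in the code and the stratification by tier. Above all, chance imbalance between randomised centres is sampling error, which the random centre term already reflects in the standard error. It is not bias on average.

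A reader might also infer that a baseline PEF exists from the meter training at Visit 0 and need only be written down. The protocol says that technique is taught, not that a value is recorded. The Time and Events Table has no PEF item at Visit 0. The best-of-three rule covers morning and evening diary readings, and SAP 5.2 rules out pre-treatment assessment of these endpoints.

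What remains is that three relevant measures are collected and unused, that text and code disagree on baseline ACT, and that the random centre term cannot absorb a systematic difference between arms arising from recruitment.

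**Conclusion.** The point holds as a modest, inexpensive improvement to four secondary analyses. The missing diary baseline, the unused Visit 0 measures and the text/code mismatch on baseline ACT are plain from the documents. The size is not: it rests on assumed ICCs of 0.01 and 0.05, assumed correlations of 0.5 to 0.7, and a covariate that acts on subject-level variance only. Under those assumptions the standard error falls by about 10-20% at ICC 0.01 and 4.5-9% at ICC 0.05. The gain shrinks as between-centre variance grows.

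A systematic recruitment difference is possible in this open-label layout, but nothing in the documents shows that one will occur. It would also be wrong to conclude that the Visit 0 data can correct for the missing baseline; they can only reduce its consequences. The primary endpoint is unaffected.

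**What to change.** In SAP 7.2.2, in both model text and code:

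- add Visit 0 FEV1 (the value that SAP 5.2 already defines as baseline) and height to the morning and evening PEF models;
- add the Visit 0 AQLQ(S) symptom-domain score to the daytime and night-time symptom models;
- list baseline ACT in the text so that it matches the code;
- state that no true diary baseline exists and that these covariates are proxies that reduce, but do not remove, starting differences.

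The code block needs editing in any case: its least-squares-means statement requests treatment by visit, while the model statement contains neither visit nor that interaction.

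No new data collection is needed. The cost is SAP wording, one or two degrees of freedom per model, and the loss of subjects with a missing Visit 0 covariate, because SAP 5.2 leaves missing baselines missing. For the symptom domain, the 90% completeness rule means at least 11 of 12 items (0.9 × 12 = 10.8). The number of subjects lost this way should be reported for each model.
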